#### **\*\*\* End Ame00163783 \*\*\***

For their appointment, participants will come to the Musculoskeletal Biomechanics and Imaging Laboratory located in the School of Kinesiology Building at the University of Michigan for one testing session lasting approximately 2 hours. All participants will be compensated for any parking expenses. Upon arrival, participants will be informed about the study procedures and have the opportunity to ask the research team questions before the start of the experiment.

Demographic data will be collected about the participant, including age, height and weight, and participants will complete a short questionnaire asking about their cancer diagnosis and treatment history. Participants will then be asked to change into a tank top. Baseline measurements of muscle stiffness and microvascular perfusion will be made with the participant sitting in a chair with the arm 90° abducted. Ultrasound shear wave elastography images will be obtained from 9 regions of the pectoralis major, one location on the serratus anterior and one location on the middle trapezius. Three images will be recorded from each location, resulting in 33 images. Ultrasound Doppler images will be obtained as a video clip as the muscle is swept top to bottom with the ultrasound transducer. The length of this video clip will vary but will be no longer than 90 seconds long and much shorter (<30 seconds) for most.

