Participants will be randomized into two groups. One group will receive the massage treatment while the massage therapist will be permitted to more readily communicate with the participant, and one group will receive the same massage treatment while the massage therapist will restrict communication with the participant to only essential exchanges. When communication is permitted, the therapist will have a short consultation with the participant, explaining the massage techniques used and asking for specific areas of shoulder/chest discomfort/pain to focus the treatment on. During the treatment, the therapist and the participant will be allowed to converse freely. The therapist will ask for feedback regarding the massage technique applied and will adjust the technique (duration, intensity) accordingly. When communication is restricted, the massage therapist will only provide essential information about the treatment (how to get ready, when treatment will start and finish) to the participant. The participant will not be instructed to limit conversation (e.g. to alert the therapist if the intensity is too much), but the therapist will limit their responses.

We will withhold information about grouping and randomization from the participants until they complete the study visit to avoid a possible confounding effect of having this knowledge. We do not expect any adverse effects from withholding this information from the participants as all participants will receive the same standardized massage treatment. All participants will be handed a sealed envelope after the study which includes a letter informing them of the restricted/unrestricted communication component of the research study as well as the group for which they had been assigned.

Randomization will be done using covariate adaptive randomization controlling for the covariates of age and body mass index. A study coordinator will randomize participants and print each participant's group membership on a piece of paper, which will be placed in a sealed envelope. The envelope will be given to the massage therapist before meeting with the participant. Only the study coordinator and the massage therapist will have knowledge of each participant's group membership. All other research personnel involved in data collection (including those actively collecting ultrasound images) and analysis will be blinded to group membership until data analysis is complete for all participants.

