## 5) Statistical Design:

The objective of this study is to assess muscle stiffness and microvascular perfusion before and after a 30-minute myofascial massage and to investigate the additional effect of patient-therapist communication. Our primary hypothesis (H1) is that muscle stiffness will be decreased and microvascular perfusion will be increased and that these effects will be enhanced when patient-therapist communication is permitted. We will test this hypothesis with a repeated-measures ANOVA. The outcome variables will be shear wave velocity as representative measure of muscle stiffness and color pixel density indicating microvascular blood flow. Time (before, immediately after, and 60 minutes after massage) will be the within-subjects factor, and communication (permitted or restricted) will be the between-subjects factor. Interaction between time and type of communication will also be assessed. Our secondary hypothesis (H2) is that scores on the Global Satisfaction with Treatment questionnaire will be higher when patient-therapist communication is permitted during the massage treatment compared to communication restricted. We will test this hypothesis with a two-sided independent t-test.

The proposed study is a pilot investigation with shear wave velocity of the pectoralis major as primary outcome. Changes in shear wave velocity after myofascial massage have not been investigated previously. Thus, a formal power analysis was not completed. We estimate that if a moderate-to-large effect size is observed ( $f = 0.25-0.4$ ), our analysis plan can detect a significant within-between interaction (e.g., time by type of communication) with 8-18 participants (assuming alpha = 0.05, power = 80%, 2 groups, 3 repeated measures and correlation = 0.7). Accounting for data loss and study dropouts, we request to recruit 30 participants to complete this work.

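### Does the missing rule for combining nine pectoralis major regions leave the primary outcome undefined?

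*Combined protocol and SAP*

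**What the plan says.** Section 5 (Statistical Design) names the primary outcome: "The proposed study is a pilot investigation with shear wave velocity of the pectoralis major as primary outcome". The analysis is a repeated-measures ANOVA in which "Time (before, immediately after, and 60 minutes after massage) will be the within-subjects factor" and communication is the between-subjects factor. Region is not a factor. Section 6 (Objectives and Endpoints) makes the before-to-after change in pectoralis major stiffness the primary objective and the comparison between communication groups a secondary one.

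The measurement text in section 4 (Experimental Design) says: "Ultrasound shear wave elastography images will be obtained from 9 regions of the pectoralis major". There are also one serratus anterior and one middle trapezius location. With three images per location, 9 × 3 = 27 of the 33 images at each time are of the pectoralis major. No section says how these 27 become one value.

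On the massage, section 4 has the therapist in the permitted arm begin with a consultation, "explaining the massage techniques used and asking for specific areas of shoulder/chest discomfort/pain to focus the treatment on", and then ask for feedback on technique and say how it is used: the therapist "will adjust the technique (duration, intensity) accordingly". For the other arm: "When communication is restricted, the massage therapist will only provide essential information about the treatment". The same section says that "all participants will receive the same standardized massage treatment". For both arms it directs the massage to the chest and shoulder on the treated side and lets the timing and order of the elements follow tissue response and patient feedback. Data collectors and analysts "will be blinded to group membership until data analysis is complete for all participants".

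**The concern.** An ANOVA with time as its only within-subjects factor needs one number per participant per time, and the plan collects nine regional values. Several single values could be defended: the mean, one region fixed in advance, the stiffest region, or the area where the participant hurts. If communication works by steering the massage to painful spots, its effect would be local and would differ between participants. A nine-region mean would dilute it, a fixed region would often miss it, and a targeted summary would capture it.

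Two things would be at stake. The primary result could depend on a choice made after the data were seen. And the effect size that a pilot passes to the next trial would be hard to interpret, since section 5 does not say to which value f = 0.25-0.4 applies.

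**Working it through.** **1. The plan's own figure.** Inputs from section 5: alpha 0.05, power 80%, 2 groups, 3 repeated measures, correlation 0.7, f = 0.25 to 0.4. For the time-by-communication interaction under sphericity, λ = f² × N × 3 / (1 − 0.7), with 2 and 2(N − 2) degrees of freedom.

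- f = 0.4, N = 8: λ = 0.16 × 8 × 3 / 0.3 = 12.8; power 81.0%.
- f = 0.25, N = 18: λ = 0.0625 × 18 × 3 / 0.3 = 11.25; power 82.5%.
- f = 0.25, N = 30: λ = 0.0625 × 30 × 3 / 0.3 = 18.75; power 97.3%.

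The stated 8-18 reproduces. The calculation uses one value per participant per time, which fits a single whole-muscle value.

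**2. Where the choice of summary matters.** Suppose k of the nine regions respond, each with effect f, and the correlation between regions is r (k and r are assumptions; the documents give neither). For the mean of nine,

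f_mean = f × (k/9) / √((1 + 8r)/9).

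Power of the interaction test with 30 analysed:

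| r | k = 9, f = 0.25 | k = 3, f = 0.25 | k = 3, f = 0.4 |
|---|---|---|---|
| 0.2 | 100% | 64% | 97% |
| 0.5 | 100% | 37% | 78% |
| 0.8 | 99% | 26% | 60% |
| 0.9 | 98% | 24% | 55% |

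With all nine regions responding, a single region has 97% and the mean 98-100%, so the choice hardly matters. With three responding regions that differ by participant and f = 0.25, simulation at r = 0.5 to 0.9 gives 19-20% for one fixed region, close to or below the mean, and 98-100% for an area named by the participant.

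**3. Can that last summary be formed?** Painful areas are asked for in the consultation only in the permitted arm. No section records the answer or maps it to the nine regions, and no research staff are in the massage room. The screening body map is used to show that pain lies in the upper quadrant. The 98-100% therefore belongs to a summary that the planned data do not appear to support in both arms. Among those the data do support, the contrast at f = 0.25 and r = 0.5 to 0.9 is 24-37% (mean) against 19-20% (fixed region).

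**4. Is the three-region case the plan's case?** If the effect occurs only in the permitted arm and equally at both later times, then f = d/√18, where d is the effect in SD units. So f = 0.25 means d = 0.25 × 4.243 = 1.06 SD in three regions and no difference between arms in the other six. Section 5 applies f to the analysed outcome. Read that way, step 1 stands and the dilution in step 2 does not enter.

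**5. Error rate.** In simulation with no true effect (r = 0.2, 0.5, 0.8), each single summary of the interaction stays at about 5%. Inflation needs selection: picking the best of four summaries (mean, maximum, stiffest region at baseline, one fixed region) gives about 16%, 13% and 9%. The plan describes no such selection.

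**The case for a change.** The strongest reply is that blinding does not cover the primary objective. The before-to-after change needs no group code, so a blinded analyst could still see which summary shows the larger fall in stiffness. A pilot's main product is also its effect size, and f is harder to carry forward if the value behind it is not named. Writing a rule down would need no extra participants, images or visits.

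The first part stands as a description: blinding limits steering of the communication comparison, not of the time effect. But it supposes an analyst who passes over the ordinary reading and looks for a favourable region, and nothing in the plan points that way. The second part is met once the report states which value was analysed.

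The argument that the arms differ by design in where the massage goes is weaker than it looks. The documents show a difference in how the focus is chosen. They do not say where the restricted-arm massage is concentrated. Tailoring to tissue response and feedback is allowed for everyone, restricted-arm participants are not told to limit conversation, and the treatment is called the same in both arms. That argument also bears on the interaction, which section 6 makes secondary, and not on the primary change over time.

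**Conclusion.** The concern does not call for a change. It is true that no section says how the nine regional values are combined, but analysts fill this gap sensibly. The outcome is named for the muscle, the model takes one value per participant per time, and the average over images and regions is the natural way to obtain it. With complete data, adding region as a within-subjects factor gives the same time-by-communication test as that mean. Following the plan on this reading keeps the 5% error rate and leaves both the 8-18 estimate and the 30 participants as they are.

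The wide spread in power rests on three assumptions from outside the documents: an effect confined to three of nine regions, the correlation between regions, and a participant-named area. Moving the correlation from 0.9 to 0.2 alone takes the mean's power from 24% to 64% at f = 0.25, and from 55% to 97% at f = 0.4. These figures show that summaries could disagree; they do not show that they will. For a pilot that states it made no formal power analysis, this is missing detail and not a fault in the design.

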## 6) Objectives and Endpoints:

OBJECTIVES	ENDPOINTS	JUSTIFICATION FOR ENDPOINTS
Primary		

OBJECTIVES	ENDPOINTS	JUSTIFICATION FOR ENDPOINTS
1. To quantify changes in muscle stiffness in response to myofascial massage.	Change in muscle stiffness of the pectoralis major will be assessed by ultrasound shear wave elastography before and after myofascial massage	Muscle stiffness is hypothesized to decrease after myofascial massage is completed compared to baseline.
Secondary		
1. To quantify changes in muscle perfusion in response to myofascial massage.	Change in muscle perfusion of the pectoralis major and upper trapezius will be assessed by Doppler imaging and superb microvascular imaging before and after myofascial massage	Perfusion to muscle tissue undergoing massage is hypothesized to increase after myofascial massage is complete compared to baseline.
2. To evaluate the effect of patient-therapist communication on changes in muscle stiffness in response to myofascial massage.	Change in muscle stiffness of the pectoralis major will be assessed by ultrasound shear wave elastography and compared between patients randomized to a group with restricted or unrestricted communication with the massage therapist.	Effects of myofascial massage on muscle stiffness is hypothesized to be enhanced in patients without restricted communication with their massage therapist.
3. To evaluate the effect of patient-therapist communication on satisfaction with treatment	Responses to the Global Satisfaction with Treatment questionnaire will be compared between patients randomized to a group with restricted or unrestricted communication with the massage therapist.	Satisfaction with treatment is hypothesized to be enhanced in patients without restricted communication with their massage therapist.

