## 1) Study Objectives:

The objective of the proposed study is to assess how myofascial massage alters stiffness and microvascular perfusion of shoulder muscles and how these changes are influenced by patient-therapist communication. Specifically, we will examine superficial shoulder muscles in breast cancer survivors before and after they receive one session of myofascial massage. Participants will be randomized 1:1 to receive massage where communication with the massage therapist is permitted or restricted. Our primary hypothesis is that stiffness of shoulder muscles will be decreased, and microvascular perfusion will be increased after a 30-minute myofascial massage, and that the addition of patient-therapist communication will result in greater changes than massage alone with patient-therapist communication restricted. Our secondary hypothesis is that treatment satisfaction will be higher when communication is permitted compared to when communication is restricted.

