The purpose of the proposed study is to establish the effect of myofascial massage on shoulder muscle properties and the interaction with patient-therapist communication in breast cancer survivors with upper quadrant myofascial pain. We will determine muscle stiffness using ultrasound shear wave elastography, a recent development that allows the non-invasive measurement of tissue stiffness *in vivo* (19). It has been shown that changes in muscle stiffness due to muscle length changes and muscle contraction can be detected with this method (20). Work from our laboratory showed increases in muscle stiffness of the pectoralis major after breast cancer treatment (21,22). Furthermore, we will determine blood flow to the treated muscles with ultrasound Doppler imaging techniques. The color pixels representing microvascular flow Doppler signals will be counted after deleting soft tissue gray-scale background in single frames of an ultrasound video (23). These techniques can non-invasively provide information about microvascular perfusion.

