After baseline measurements are completed, participants will be taken to the massage room where they will meet the massage therapist. Participants will be asked to remove all upper body clothing before lying down face up on the massage bed. They will be asked to cover their bodies, including chest and shoulders, with a sheet and woolen blanket. The massage therapist will leave the room while the participants get ready. Once the participant is ready, the massage therapist will re-enter the room and begin the myofascial massage. The treatment will last 30 minutes and focus on the chest and shoulder of the side that received the cancer treatment. Techniques applied during the intervention will include skin glide (variable time), stroking (2-3 minutes), scar tissue rolling (2-3 minutes), strumming (2-3 minutes), fascial stretch (3-5 minutes), circular friction (1-2 minutes), deep fascial release (3-5 minutes) and arm pull (60 seconds). The timing and order of each element will be varied based on tissue response and patient feedback. The massage therapist will carefully expose areas of the chest and/or shoulder to perform the treatment. A massage oil may be applied to the participant's skin if necessary. After the conclusion of the massage treatment, the massage therapist will leave the room so that the participant can get dressed again. No research personnel will be present in the massage room during the entire time.

Immediately afterward, participants will return to the examination room, where the measurements conducted at baseline will be repeated. Participants will then remain in the clinical suite (or an adjacent waiting room) for 60 minutes, after which all measurements will be repeated a second time. During their 60-minute wait period, participants will be asked to fill in the treatment satisfaction questionnaire. Additionally, participants will be allowed to keep themselves occupied (e.g., reading), and they will be allowed to use the TV entertainment system provided in the examination room.

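### The before-to-after change is presented as an effect of massage, but every participant is massaged and no untreated reference is planned, so the primary objective and secondary objective 1 can only be descriptive

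*Combined protocol and SAP*

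**What the plan says.** Section 6 gives the primary objective as "To quantify changes in muscle stiffness in response to myofascial massage". Its endpoint is pectoralis major stiffness, which "will be assessed by ultrasound shear wave elastography before and after myofascial massage". Secondary objective 1 has the same form for perfusion. Section 3 is more explicit: "The purpose of the proposed study is to establish the effect of myofascial massage on shoulder muscle properties".

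The allocation is described in Section 1: "Participants will be randomized 1:1 to receive massage where communication with the massage therapist is permitted or restricted". Section 4 (Experimental Design) adds that "all participants will receive the same standardized massage treatment", and on the side treated: "The treatment will last 30 minutes and focus on the chest and shoulder of the side that received the cancer treatment".

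Section 4 describes one baseline scan, one scan straight after the massage and one scan 60 minutes later. Section 5 analyses these with a repeated-measures ANOVA: "Time (before, immediately after, and 60 minutes after massage) will be the within-subjects factor". Communication is the between-subjects factor, and the interaction of the two is also assessed.

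**The concern.** The objectives in Sections 3 and 6 use causal language about massage, but massage does not vary between participants. The only information on it is the time factor, which carries everything that happens between scans. Between the first and second scans each participant lies face up for the 30-minute session, dresses and is scanned again. A 60-minute wait and a third scan follow.

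A significant time effect would probably be reported as an effect of massage on the primary endpoint. The design supports a narrower statement: stiffness or perfusion changed across a visit that included massage. The difference matters because Section 3 motivates the study by the unclear mechanism of massage benefit. A change that rest or repeat measurement could also produce does not settle that question. Drift in the opposite direction could equally hide a real massage effect.

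**Working it through.** **1. Is any untreated reference planned?**
- Arms: two, both massaged (Sections 1 and 4).
- Stiffness sites per scan (Section 4): 9 pectoralis major + 1 serratus anterior + 1 middle trapezius = 11 locations. 11 × 3 images = 33, the stated total, so there is no second set for the other side.
- Scans: one before and two after. There is no repeat baseline and no rest period before treatment.
- No site is designated as a reference in Section 4, 5 or 6.

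**2. What each contrast estimates.** Write *m* for the massage effect, *δ* for change from any other cause common to both arms, and *c* for the added effect of each communication condition.
- Change, permitted arm: *m* + *δ* + *c*(permitted).
- Change, restricted arm: *m* + *δ* + *c*(restricted).
- Average over arms (the time effect): *m* + *δ* + mean *c*. Here *m* and *δ* cannot be separated.
- Difference between arms (time by communication): *c*(permitted) − *c*(restricted). Here *δ* cancels.

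**3. The plan's own figure.** Section 5 gives 8–18 participants for 80% power, f = 0.25–0.4, alpha 0.05, 2 groups, 3 measures and correlation 0.7. Use the noncentral F with λ = f²·N·3/(1 − 0.7), df1 = 2, df2 = 2(N − 2), under sphericity.
- f = 0.25, N = 18: λ = 0.0625 × 18 × 3/0.3 = 11.25, power 82.5% (N = 16 gives 76.9%).
- f = 0.4, N = 8: λ = 0.16 × 8 × 3/0.3 = 12.8, power 81.0% (N = 6 gives 62.2%).

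The figure reproduces. It concerns the interaction, not the time effect in the primary objective.

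**4. Illustration of scale.** The drift size *d* is an assumption, taken over 0.1 to 0.5 baseline SD. Also assumed: *m* = 0, all 30 complete, correlation 0.7, two-sided 0.05.
- SD of a before-to-after change = √(2 × (1 − 0.7)) = √0.6 = 0.775 baseline SD.
- Paired t noncentrality = (*d*/0.775) × √30, on 29 df.
- For comparison, the ANOVA time test with the same drift at both later scans: f² = 2*d*²/9, λ = (2*d*²/9) × 30 × 3/0.3 = 66.7*d*², on 2 and 56 df.

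| Assumed drift (SD) | Noncentrality, paired t | Chance of p<0.05, paired t | Chance of p<0.05, ANOVA time test |
|---|---|---|---|
| 0.1 | 0.71 | 10.5% | 10.1% |
| 0.2 | 1.41 | 27.7% | 27.6% |
| 0.3 | 2.12 | 53.6% | 56.0% |
| 0.4 | 2.83 | 78.0% | 82.0% |
| 0.5 | 3.54 | 92.7% | 95.4% |

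A larger sample does not help: at 0.2 SD the paired-t rate is 17.9% with 18 participants and 27.7% with 30.

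**The case against.** The best defence is that this is a declared pilot whose uncontrolled before-after component is visible, and that much of the operational text is already descriptive. The endpoints are changes from before to after, compared with baseline. That stands: a single-group estimate is acceptable in a pilot. It does not justify a stated purpose of establishing an effect, and no section acknowledges the limit.

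Some of the possible alternative explanations are weak:
- **Scan posture.** A reader might infer that position differs between scans. It does not: participants are seated with the arm abducted at baseline and the same measurements are repeated. Only the recumbent period in between is at issue.
- **Warmth.** Section 4 says of participants, "They will be asked to cover their bodies, including chest and shoulders, with a sheet and woolen blanket", which suggests warming. The same section has the therapist expose parts of the chest or shoulder to treat them, so the treated area is uncovered for at least part of the session.
- **The session as a package.** Lying draped on a table can be seen as part of massage as delivered. That is a fair estimand, but the objective would have to say so, and elapsed time and repeat scanning would still be mixed in.

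The drift rates describe any uncontrolled before-after study with an assumed drift and no true effect. They are not evidence about this trial. Drift would also have to run in the predicted direction (stiffness down, perfusion up) to pass for the hypothesised result.

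The 60-minute scan is not a control. A return to baseline fits a passing effect of rest as well as a passing effect of massage.

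**Conclusion.** The concern holds for the primary objective and secondary objective 1. The time effect that answers them cannot separate massage from recumbent rest, elapsed time and repeat scanning, so the causal wording claims something the design cannot deliver. This follows from the allocation and the measurement schedule and needs no numerical assumption.

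The size of any resulting error is unknown. The range of 10.5% to 93% is illustrative and rests on an assumed drift of 0.1 to 0.5 baseline SD, correlation 0.7, 30 completers, a paired t-test and no massage effect. Section 5 set 30 to allow for losses, so fewer may complete.

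Two stronger readings are tempting and not supported. One is that the communication result is compromised too. It is not, on this ground, because drift common to both arms cancels in the randomised comparison. The other is that an observed change would be false, or that the study needs an unmassaged arm to be worth doing. The documents give no drift size, and a pilot may report a before-to-after change if it is described as such.

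**What to change.** **Change the wording in Sections 1, 2, 3 and 6**, and align the Synopsis objective:
- Restate the primary objective and secondary objective 1 as descriptive, for example: *to describe the change in pectoralis major stiffness (perfusion) from before to after a session that includes myofascial massage.*
- Replace the Section 3 statement about establishing the effect of massage.
- State that only the communication comparison is a randomised causal contrast, and that the time effect may include rest, elapsed time and repeat scanning.

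The cost is a weaker claim. Data collection and analysis do not change.

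**Do not use middle trapezius as an untreated reference**, although it is already imaged. Section 6 lists upper trapezius among the perfusion muscles and describes that endpoint as tissue undergoing massage, so subtracting trapezius change could remove real effect. Middle trapezius is also documented only for elastography, with 1 location (3 images) against 9 (27 images) for pectoralis major.

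**Untreated-side scanning is optional**, for a later study or if visit time allows. Eligibility requires a unilateral diagnosis, so an untreated side would normally exist. The visit is about 120 minutes; 120 − 30 (massage) − 60 (wait) leaves about 30 minutes for demographics, the history questionnaire, changing and three scan sessions. Extra scanning could also delay the scan that is meant to follow straight after massage.
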